12.5 Analysis of secondary endpoints

The secondary objectives for the study are to evaluate complete pathologic response (pCR) rate following neoadjuvant capmatinib therapy, overall response rate (ORR) and safety and tolerability for each cohort.

12.5.1 Secondary Efficacy endpoint(s)

The secondary efficacy endpoints will be assessed using the Full Analysis Set (FAS). The following analyses will be performed for each cohort:

Complete Pathologic response (pCR) rate is defined as the proportion of participants with no residual viable cancer cells. pCR rate will be assessed via both central and local review. pCR rate will be summarized using binomial response rate and its 95% confidence interval will be presented for each cohort following neoadjuvant capmatinib therapy using Coppler-Pearson method.

Overall response rate (ORR) is defined as the proportion of participants with best overall response (BOR) of complete response (CR) or partial response (PR) according to RECIST v 1.1. ORR will be calculated using local investigator review.

ORR will be summarized using binomial response rate and its 95% confidence interval will be presented each cohort using Coppler-Pearson method.

Disease Free Survival (DFS) is defined as the time from date of end of adjuvant therapy with capmatinib to the date of event defined as the recurrence of cancer or death due to any cause. Disease free survival will be presented at 24, 36 and 60 months after adjuvant capmatinib treatment for each cohort. The disease free survival distribution will be estimated using the Kaplan-Meier method, and the estimates of the 25th, median and 75th percentile of the DFS and 95% confidence intervals will also be presented.

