1.2 Purpose

Activation of the MET pathway is associated with many cancers and can be caused by MET exon 14 skipping mutation (METex14), overexpression and gene amplification. METex14 occur in 3–4% and MET amplifications in 1–6% of participants with NSCLC (Paik et al 2015, Saigi et al. 2018, Guo et al. 2019). Capmatinib is approved in the United States for the treatment of metastatic NSCLC with METex14 mutation and has an adverse event profile that is manageable and not expected to complicate surgery (Wolff et al. 2019, Paik et al 2020). The current study will determine if neoadjuvant capmatinib can improve the major pathological response (MPR) in participants with stages IB-IIIA, N2 and selected IIIB (T3N2 or T4N2) lung cancers with MET exon 14 mutations and/or high MET amplification beyond those achieved with surgery, chemotherapy, and radiation. Treatment will continue with capmatinib in the adjuvant setting to evaluate the potential clinical benefit of extended therapy and allow longer follow up in order to assess disease free survival

[figure not shown]
2 Objectives and endpoints

Objectives and related endpoints are described in [Table 2-1](#) below.

Table 2-1 Objectives and related endpoints

Objective(s)	Endpoint(s)
Primary objective(s)	Endpoint(s) for primary objective(s)
To determine the MPR in resection specimens following neoadjuvant capmatinib in 2 cohorts. Cohort A: MET exon 14 skipping mutation, irrespective of MET GCN; Cohort B: High MET amplification (MET: GCN \geq 10)	MPR rate in each cohort based on local review, defined as the percentage of participants with \leq 10% residual viable cancer cells
Secondary objective(s)	Endpoint(s) for secondary objective(s)
To assess overall response rate post neoadjuvant treatment with capmatinib in each cohort	Overall response rate (ORR) based on local investigator assessment per RECIST 1.1
To determine the complete pathologic response following neoadjuvant capmatinib therapy in each cohort	Complete pathologic response (pCR) rate based on local review
To evaluate safety and tolerability of capmatinib	Type, frequency and severity of AEs [CTCAE] v5.0), vital signs and laboratory abnormalities

Objective(s)	Endpoint(s)
To assess disease free survival with adjuvant therapy with capmatinib	Disease free survival rate at 24, 36, and 60 months

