9.1 Discontinuation from study treatment and from study

9.1.1 Discontinuation from study treatment

Discontinuation of study treatment for a participant occurs when study treatment is permanently stopped for any reason (prior to the planned completion of study drug administration) and can be initiated by either the participant or the investigator.

The investigator must discontinue study treatment for a given participant if, he/she believes that continuation would negatively impact the participant's well-being.

Discontinuation from study treatment is required under the following circumstances:

- Participant/guardian decision
- Investigator decision
- Pregnancy (see [Section 10.1.4](#))
- Any situation in which continued study participation might result in a safety risk to the participant
- Disease recurrence
- AE requiring permanent discontinuation of study treatment (see [Table 6-3](#))
- Protocol deviation that results in a significant risk to participant's safety
- Withdraw of consent (see [Section 9.1.3](#))
- Study is terminated by the sponsor (see [Section 9.1.5](#))
- Death
- Lost to follow-up (see [Section 9.1.4](#))

If discontinuation of study treatment occurs, the investigator should make a reasonable effort to understand the primary reason for the participant's premature discontinuation of study treatment and record this information.

Participants who discontinue study treatment or who decide they do not wish to participate in the study further should NOT be considered withdrawn from the study UNLESS they withdraw their consent (see [Section 9.1.3](#)). **Where possible, they should return for the EOT assessments indicated in [Table 8-1](#) and safety follow-up.** If they fail to return for these assessments for unknown reasons, every effort (e.g. telephone, e-mail, letter) should be made to contact the participant/pre-designated contact as specified in the lost to follow-up section. This contact should preferably be done according to the study visit schedule.

If the participant cannot or is unwilling to attend any visit(s), the site staff should maintain regular telephone contact with the participant, or with a person pre-designated by the participant. This telephone contact should preferably be done according to the study visit schedule.

After study treatment discontinuation, in abbreviated visits, the data mentioned in [Table 8-1](#) should be collected at clinic visits or via telephone/email contact.

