16.2.3.2 Time to event variables

16.2.3.2.1 Progression-free survival

Usually in all Oncology studies, participants are followed for tumor progression after discontinuation of study medication for reasons other than progression or death. If this is not used, e.g. in Phase I or II studies, this should be clearly stated in the protocol. Note that randomized trials (preferably blinded) are recommended where PFS is to be the primary endpoint.

Progression-free survival (PFS) is the time from date of randomization/start of treatment to the date of event defined as the first documented progression or death due to any cause. If a patient has not had an event, progression-free survival is censored at the date of last adequate tumor assessment.

PFS rate at x weeks is an additional measure used to quantify PFS endpoint. It is recommended that a Kaplan Meier estimate is used to assess this endpoint.

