16.2.3.2.8 Definition of start and end dates for time to event variables

Assessment date

For each assessment (i.e. evaluation number), the **assessment date** is calculated as the latest of all measurement dates (e.g. X-ray, CT-scan) if the overall lesion response at that assessment is CR/PR/SD/UNK. Otherwise - if overall lesion response is progression - the assessment date is calculated as the earliest date of all measurement dates at that evaluation number.

In the calculation of the assessment date for time to event variables, any unscheduled assessment should be treated similarly to other evaluations.

Start Dates

For all “time to event” variables, other than duration of response, the randomization/ date of treatment start will be used as the start date.

For the calculation of duration of response the following start date should be used:

- Date of first documented response is the assessment date of the first overall lesion response of CR (for duration of overall complete response) or CR / PR (for duration of overall response) respectively, when this status is later confirmed.

End dates

The end dates which are used to calculate ‘time to event’ variables are defined as follows:

- Date of death (during treatment as recorded on the treatment completion page or during follow-up as recorded on the study evaluation completion page or the survival follow-up page).
- Date of progression is the first assessment date at which the overall lesion response was recorded as progressive disease.
- Date of last adequate tumor assessment is the date the last tumor assessment with overall lesion response of CR, PR or SD which was made before an event or a censoring reason occurred. In this case the last tumor evaluation date at that assessment is used. If no post-baseline assessments are available (before an event or a censoring reason occurred) the date of randomization/start of treatment is used.
- Date of next scheduled assessment is the date of the last adequate tumor assessment plus the protocol specified time interval for assessments. This date may be used if back-dating is considered when the event occurred beyond the acceptable time window for the next tumor assessment as per protocol (see [Section 16.2.3.2.8](#)).

Example (if protocol defined schedule of assessments is 3 months): tumor assessments at baseline - 3 months - 6 months - missing - missing - PD. Date of next scheduled assessment would then correspond to 9 months.

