16.2.4.5.1 Calculation of time to event variables

Time to event = end date - start date + 1 (in days)

When no post-baseline tumor assessments are available, the date of randomization/start of treatment will be used as end date (duration = 1 day) when time is to be censored at last tumor assessment, i.e. time to event variables can never be negative.

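### Does the protocol's start of disease-free survival at the end of adjuvant capmatinib call for a change to the plan?

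*Protocol*

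**What the plan says.** Protocol 12.5.1 defines the endpoint: "Disease Free Survival (DFS) is defined as the time from date of end of adjuvant therapy with capmatinib to the date of event". The event is recurrence or death from any cause. The next sentence agrees on the origin: "Disease free survival will be presented at 24, 36 and 60 months after adjuvant capmatinib treatment for each cohort". The analysis set is the Full Analysis Set (FAS), which requires only one dose of capmatinib (Protocol 12.1.1).

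The objective in Protocol Table 2-1 reads "To assess disease free survival with adjuvant therapy with capmatinib". Its endpoint column gives the three landmarks without an origin, and SAP Table 1-1 repeats it.

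Protocol Appendix 2 holds general rules for time-to-event variables. For variables "other than duration of response, the randomization/ date of treatment start will be used as the start date" (16.2.3.2.8). Times are computed as end date minus start date plus one day (16.2.4.5.1).

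Follow-up after adjuvant treatment is two years for survival in the protocol summary and Section 3, but 30 days for safety in Protocol 9.2 and SAP 1.1. Recurrence imaging is scheduled only during adjuvant treatment (Protocol 8.3.1, Table 8-2).

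SAP Sections 1, 2.2, 2.7.1, 2.7.2 and 4 replace the protocol's analyses with listings, because 4 participants were enrolled. SAP 2.7.3 marks missing-data and censoring rules for the secondary endpoints as not applicable.

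**The concern.** DFS with adjuvant therapy should count recurrences while patients are on that therapy. A clock that starts when therapy ends does the reverse. Protocol 9.1.1 puts disease recurrence on a list headed "Discontinuation from study treatment is required under the following circumstances", so a recurrence on treatment itself brings about time zero and is dated at or close to it, often before it. Section 12.5.1 has no rule for such events, none for FAS participants who never restart capmatinib, and no censoring rule. Two of the three landmarks lie beyond any follow-up the documents describe.

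Had a Kaplan-Meier curve been drawn on this definition, the result would have depended on programming choices made after the data were seen. Dropping on-therapy recurrences and scoring them as day-1 events give different curves, and neither measures what the objective asks.

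**Working it through.** There is no stated figure to reproduce. The check compares the origin with follow-up, event timing and imaging, and then asks which output uses it.

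**1. Follow-up after time zero, for a completer**

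| Landmark | Two-year follow-up (24 months) | 30-day follow-up (about 1 month) |
|---|---|---|
| 24 months | 24 − 24 = 0; just reached | not reached |
| 36 months | 36 − 24 = 12 months short | not reached |
| 60 months | 60 − 24 = 36 months short | not reached |

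With three years of adjuvant treatment, the 60-month landmark needs 36 + 60 = 96 months from adjuvant start, against 36 + 24 = 60 planned. That the planned total is exactly 60 suggests the landmarks were meant to run from about surgery or adjuvant start. This is inference; no passage says so.

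**2. Recurrence on therapy.** If the scan is *d* days before the last dose, end − start + 1 gives 1 − *d*:

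- *d* = 0: 1 day
- *d* = 1: 0 days
- *d* = 7: −6 days
- *d* = 14: −13 days

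Appendix 2 remarks that "time to event variables can never be negative". In its place (16.2.4.5.1) that explains the fallback for times censored without any post-baseline tumor assessment. It is not a rule for events before the origin.

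**3. Participants without an origin.** The list of supportive analyses under Protocol 12.4.5 expects some patients to have no adjuvant therapy, or chemotherapy alone. They belong to the FAS but have no end of adjuvant capmatinib.

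**4. Is Appendix 2 contradicted?** Not bindingly. It is a generic guideline for solid-tumor studies. Section 16.2.4 offers its data-handling rules as guidance, and 16.2.4.1 leaves study-specific decisions to the protocol or analysis plan. It never defines DFS. A study-specific definition may depart from its default, so the real conflict is with the objective.

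**5. Would event-free completers be censored before time zero?** Only if DFS borrows the Appendix 2 rule for PFS: "If a patient has not had an event, progression-free survival is censored at the date of last adequate tumor assessment". Even then it depends on the scan date. Assume no chemotherapy, capmatinib restarted at week 10, and three adjuvant years (1,095.75 / 7 = 156.5 weeks), so treatment ends at week 166.5.

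- 26-weekly scans counted from one year after restart: the last is at week 166, about 4 days before the last dose. With the ±7-day window it may fall up to 3 days after.
- 26-weekly scans counted from the week-58 scan: the last is at week 162, about 32 days before.

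So this part holds under some readings and not others.

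**6. What uses the origin?** SAP 2.7.1 lists tumor assessments and investigator responses. SAP 2.1.1 counts study day from the first dose. No DFS time, curve or landmark rate is produced, so the number of outputs that depend on 12.5.1 is zero.

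**7. Is a repair simple?** Two candidates:

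- *Start of adjuvant capmatinib.* Vital status fits all three landmarks with three adjuvant years plus two years of follow-up (60 months). Protocol 6.1.5 instead caps treatment at three years after surgery. With a restart at week 10 (2.3 months) that gives 36 − 2.3 + 24 = 57.7 months. With the 30-day version, follow-up ends near 37 months.
- *Surgery.* This covers resected patients who never restart. A patient with no adjuvant treatment may have no scan after surgery. If the preoperative scan, 1 to 7 days before surgery, were taken as the last assessment, the censored time would be 1 − *d* = 0 to −6 days. A further rule, such as censoring at day 1, would be needed.

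Either repair also requires the follow-up and treatment-duration statements to be reconciled.

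**The case for a change.** The strongest argument for acting is that this is more than a slip. Two consecutive sentences in 12.5.1 agree on the origin, and they are the only study-specific definition behind an endpoint that SAP Table 1-1 still carries. The SAP appendix feeds the clinical study report, and Protocol 13.3 promises public posting of results. A footnote to Table 1-1 giving a corrected origin and stating that DFS was not estimated would cost little.

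The diagnosis stands: as written, the definition is unusable and misses the objective. The case for action does not. That DFS is not analyzed, and why, is already stated in SAP 2.7.1 and Section 4. A new origin in a SAP footnote, with 12.5.1 unchanged, would make the two documents disagree about an analysis nobody will run. Changing 12.5.1 itself needs a written amendment with approvals (Protocol 14.1). The missing censoring rule is a matter the protocol leaves to the SAP (Protocol Section 12), and SAP 2.7.3 closes it as not applicable.

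**Conclusion.** No change, because there is nothing to gain. Protocol 12.5.1 starts the DFS clock at the wrong end of adjuvant treatment. It leaves some FAS participants without an origin, puts on-therapy recurrences at, near or before time zero, and sets landmarks 12 and 36 months beyond the longer stated follow-up. Its effect on reported results is zero, since the final SAP estimates no DFS and lists data for 4 participants by study day from first dose. No size of bias is claimed. The documents give no hazard or relapse horizon from which to derive one.

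This rests on the SAP's cancellation of the analysis holding. If DFS were ever to be estimated from these data, the origin would have to be settled first (start of adjuvant capmatinib or surgery), with day-1 censoring for anyone lacking a later assessment. The two-year and 30-day follow-up statements, and the two statements of treatment duration (Protocol Section 3 and 6.1.5), would have to be reconciled.

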12.5.2 Safety endpoints

For all safety analyses, the safety set will be used and data will be presented for each cohort. Listings and tables will also be presented by each cohort for all participants.

The overall observation period will be divided into three mutually exclusive segments:

1. Pre-treatment period: from the day of subject's informed consent to the day before first dose of study medication.
2. On-treatment period: from day of first dose of study medication to 30 days after the date of last actual administration of any study medication.
3. Post-treatment period: starting at day 31 after last dose of study medication.

If dates are incomplete in a way that clear assignment to pre-, on-, or post-treatment period cannot be made, then the respective data will be assigned to the on-treatment period. Additional details to address incomplete AE and/or dosing dates will be addressed in the SAP.

Additional summaries will be displayed to report deaths, all AEs, AEs related to study treatment, all SAEs and SAEs related to study treatment collected up to 30 days after last administration of any study treatment.

Adverse events

Summary tables for AEs will include only AEs that started or worsened during on-treatment periods, the treatment-emergent AEs and will be presented for each cohort.

The incidence of treatment-emergent AEs will be summarized by system organ class and preferred term, severity (based on CTCAE v 5.0 grades), types of adverse event, and relation to study treatment.

Serious adverse events (SAEs), non-serious adverse events, and adverse events of special interest (AESI) during the on-treatment period will be tabulated.

All reported deaths (on-treatment and post-treatment) will be summarized.

All AEs, deaths and serious adverse events (including those from the pre and post-treatment periods) will be listed and those starting during the pre-treatment and post-treatment period will be flagged.

Vital signs

Data on vital signs will be tabulated and listed for each cohort, notable values will be flagged.

12-lead ECG

12- lead ECGs including PR, QRS, QT, QTcF, and HR intervals will be obtained for each participant during the study. ECG data will be read and interpreted locally.

Categorical analysis of QT/QTc interval data based on number of participants meeting or exceeding predefined limits in terms of absolute QT/QTc intervals or changes from baseline will be presented for each cohort. In addition, a listing of these participants will be produced. All ECG data will be listed by subject and visit/time, abnormalities will be flagged.

Clinical laboratory evaluations

Grading of laboratory values will be assigned programmatically as per NCI CTCAE version 5.0. The calculation of CTCAE v 5.0 grades will be based on the observed laboratory values only, clinical assessments will not be taken into account.

CTCAE v 5.0 grade 0 will be assigned for all non-missing values not graded as 1 or higher. Grade 5 will not be applicable.

For laboratory tests where grades are not defined by CTCAE v 5.0, results will be categorized as low/normal/high based on laboratory normal ranges.

The following listing/summaries will be generated separately for hematology, and biochemistry tests:

- Listing of all laboratory data with values flagged to show the corresponding CTCAE v 5.0 grades, if applicable and the classifications relative to the laboratory normal ranges.

For laboratory tests where grades are defined by CTCAE v 5.0:

- Worse post-baseline CTCAE v 5.0 grade (regardless of the baseline status). Each subject will be counted only once for the worst grade observed post-baseline.
- Shift tables using CTCAE v 5.0 grades to compare baseline to the worst on-treatment value.

For laboratory tests where grades are not defined by CTCAE v 5.0:

[figure not shown]
- Shift tables using the low/normal/high/(low and high) classification to compare baseline to the worst on-treatment value.

Other safety evaluations

Tolerability

[figure not shown]
Tolerability of study drug treatment will be assessed by summarizing the number of treatments, dose interruptions and dose reductions. Reasons for dose interruption and dose reductions will be listed by subject and summarized for each cohort.

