2.2 Secondary estimands

No secondary estimands planned in this study.

[figure not shown]
3 Study design

This is a phase II, two-cohort, two-stage, study of capmatinib given for 8 weeks (2 cycles) prior to surgical resection, followed by three years capmatinib treatment in adjuvant setting. Surgery should be performed up to 2 weeks after the last dose of neoadjuvant study treatment. Please contact the sponsor if surgery will be beyond the 2 week window.

There will be 2 molecularly defined cohorts enrolling in parallel: Cohort A: MET exon 14 skipping mutations, irrespective of MET GCN or Cohort B: high level MET amplification (MET: GCN ≥ 10 by FISH or FoundationOne CDx NGS using tumor tissue). [REDACTED]

[figure not shown]
[REDACTED] Participants who have both MET exon 14 skipping mutations and high level

MET amplification (MET: GCN ≥ 10 by FISH or FoundationOne CDx NGS using tumor tissue) will be enrolled into Cohort A. An evaluable subject will undergo the neoadjuvant treatment and undergo surgery with a pathological response report analysis.

After surgery, participants will continue onto 3 years of adjuvant capmatinib therapy, followed by two years of survival follow-up.

Figure 3-1 Study design

*Adjuvant chemotherapy is optional and at the discretion of the treating physician. See section [6.2.1.2](#) for further details.

4 Rationale

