6.1 Study treatment

The investigational drug to be used in this study is capmatinib, as described in [Table 6-1](#). The study treatment is defined as capmatinib administered orally as a single agent.

Capmatinib will be labeled and provided to sites by Novartis in compliance with US regulations.

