6.2.1.1 Adjuvant chemotherapy

Standard postoperative adjuvant chemotherapy, consisting of a platinum-based doublet for 4 cycles is allowed. For patients receiving adjuvant chemotherapy no more than 26 weeks can elapse between surgery and start of adjuvant capmatinib.

Chemotherapy regimen, dosing, start and stop dates must be recorded in the eCRF.

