6.5.1 Treatment interruption and treatment discontinuation

If the administration of capmatinib is temporarily interrupted for reasons other than toxicity, then treatment with capmatinib may be resumed at the same dose. If the treatment with capmatinib is withheld due to toxicity, the dose modification guidelines in [Table 6-3](#) & [Table 6-2](#) should be followed. In any case, scheduled visits and all assessments (including tumor assessments) should continue to be performed, as described in [Table 8-1](#).

If the treatment with capmatinib is withheld for more than 21 consecutive days (counting from the first day when a dose was interrupted), excluding the surgical and adjuvant chemotherapy

window specified below, then capmatinib should be permanently discontinued. Under exceptional circumstance, when the investigator believes that continuing treatment may still derive clinical benefit for the participant, study treatment may be resumed. However, the investigator must discuss and receive approval from Novartis Medical Lead or designee prior to continuing capmatinib treatment.

Participants who discontinue the study due to a study drug related AE or an abnormal laboratory value must be followed as described in [Section 6.5.2](#).

After the 8 week neoadjuvant treatment with capmatinib, participants are to undergo surgical resection. Participants should undergo within 2 weeks after last dose of neoadjuvant capmatinib. In addition, participants may receive adjuvant chemotherapy prior to re-starting capmatinib at the discretion of the investigator. For patients who do not receive adjuvant chemotherapy no more than 10 weeks should elapse from the date of surgery and the start of adjuvant capmatinib. For patients who do receive adjuvant chemotherapy, see [Section 6.2.1.1](#) for the dosing window. If participants for any reason cannot re-start capmatinib therapy within the specified windows, then study treatment must be permanently discontinued.

Participants who discontinue the study due to a surgery related AE must complete the EOT visit and safety follow-up visit.

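### In the visible text, the on-treatment window counts surgery- and chemotherapy-period adverse events up to restart for participants who resume capmatinib, but only to day 30 for those who do not

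*Protocol*

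**What the plan says.** **The window.** Protocol Section 12.5.2 sets a single interval: "On-treatment period: from day of first dose of study medication to 30 days after the date of last actual administration of any study medication". The post-treatment period begins on day 31. AE summary tables take only events that start or worsen on treatment. Deaths in both periods are summarised, and all AEs are listed, with those starting before or after the on-treatment period flagged.

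**What counts as study medication.** Section 6.1: "The study treatment is defined as capmatinib administered orally as a single agent". Adjuvant chemotherapy therefore does not extend the window.

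**The planned gap.** Section 3: "Surgery should be performed up to 2 weeks after the last dose of neoadjuvant study treatment". Without chemotherapy, Section 6.5.1 says "no more than 10 weeks should elapse from the date of surgery and the start of adjuvant capmatinib". With chemotherapy, Section 6.2.1.1 says: "For patients receiving adjuvant chemotherapy no more than 26 weeks can elapse between surgery and start of adjuvant capmatinib". When Section 6.5.1 limits withholding to 21 consecutive days, it does so "excluding the surgical and adjuvant chemotherapy" window, so the protocol itself treats this gap as different from an ordinary interruption.

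**Participants who do not resume.** Section 6.5.1: "If participants for any reason cannot re-start capmatinib therapy within the specified windows, then study treatment must be permanently discontinued". Their last actual dose is then the last neoadjuvant dose.

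**The SAP.** Section 4 replaces the planned summaries with listings because only 4 participants were enrolled. Section 2.8.1 still plans three AE tables for the public registry: non-serious on-treatment AEs at or above 5%, on-treatment SAEs, and SAEs suspected to be related. The visible text does not redefine the window or split it by phase.

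**The concern.** Whether a postoperative or chemotherapy-period event enters the on-treatment tables depends on something that happens after it: a later capmatinib dose. Two participants with the same complication on the same postoperative day can be handled differently. Someone kept from restarting by surgical complications or chemotherapy toxicity is exactly the person whose later non-fatal events drop out. For someone who restarts, AEs arising during platinum chemotherapy, weeks off capmatinib, are counted as on-treatment for capmatinib.

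Safety and tolerability is a secondary objective, and Protocol Section 1.2 states that the AE profile is not expected to complicate surgery. Perioperative events bear directly on that expectation. The registry tables are the only AE tables the visible SAP still plans, and two of the three are all-causality.

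**Working it through.** The plan gives no figure of its own on this point, so there is nothing to reproduce. The check is date arithmetic on the protocol's own limits.

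**Inputs.** Day 0 is the last neoadjuvant dose.
- Surgery day *s*: 0 to 14 (Section 3).
- Limit from surgery to restart, *r*: 10 × 7 = 70 days without chemotherapy (Section 6.5.1); 26 × 7 = 182 days with it (Section 6.2.1.1).
- Tail after the last dose: 30 days (Section 12.5.2).

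**Formulas.**
- Off-drug gap with restart at the limit = *s* + *r*
- Part of the gap beyond the tail = *s* + *r* − 30
- Postoperative gap days counted, restarter = *r*
- Postoperative days counted, non-restarter = 30 − *s*

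| Surgery day | Chemotherapy | Gap | Beyond day 30 | Counted, restarter | Counted, non-restarter | Ratio |
|---|---|---|---|---|---|---|
| 0 | no | 70 | 40 | 70 | 30 | 2.3 |
| 0 | yes | 182 | 152 | 182 | 30 | 6.1 |
| 14 | no | 84 | 54 | 70 | 16 | 4.4 |
| 14 | yes | 196 | 166 | 182 | 16 | 11.4 |

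With surgery on day 14, the share of the gap beyond the tail is 54/84 = 64% without chemotherapy and 166/196 = 85% with it.

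**Lower end.** If restart is on or before day 30, no gap day lies beyond the tail and the excess is zero.

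**Later surgery.** Table 8-1, footnote 6, accepts surgery beyond 2 weeks, though it should be avoided. At day 28 a non-restarter has 30 − 28 = 2 postoperative days counted. After day 30 the operation itself falls outside that participant's window.

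**Check of the remedy.** If the 30-day tail is applied after each course, both groups have 30 − *s* postoperative days counted in the gap. The restarter's other *s* + *r* − 30 days go to a separate column. Since (30 − *s*) + (*s* + *r* − 30) = *r*, no day now counted is lost.

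**The case against.** The case against giving this much weight is strong.

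- One overall window is simple and contradicts no other passage.
- With 4 enrolled, one participant is 1/4 = 25%, so the 5% registry threshold filters nothing and extra columns would be nearly empty. Dated AE listings, together with the dosing and procedure listings, let a reader place each event by hand.
- Deaths are summarised in both periods, post-treatment AEs are already to be flagged in the protocol's listing, and the related-SAE table deals with attribution for SAEs.
- Part of the imbalance is one of collection. Section 10.1.1 requires AE monitoring only for at least 30 days after the last dose. Sections 8.6.1 and 10.1.3 restrict collection to SAEs suspected to be related once a new antineoplastic therapy begins. No table definition recovers events that were never recorded.

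All of this stands and keeps the point small. It does not remove it: the registry reader sees tables, and the all-causality ones inherit the definition.

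Three stronger readings are tempting but not supported:

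- *That no phase split exists.* SAP Section 2.1 breaks off into redacted text where it turns to the limited numbers, and the TFL and PDS module named in SAP Section 2.1.1 is not available.
- *That non-restarters are followed for months after their window closes.* Section 8.6.1 does count follow-up from the EOT visit. But Section 8 wants that visit as soon as possible after discontinuation, Appendix Section 16.2.4.2 places it within 7 days of last treatment, and Section 6.5.2, Section 10.1.1 and Table 8-1 count from the last dose. No firm figure can rest on this.
- *That the ratios measure AEs.* They compare calendar days at the permitted extremes.

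**Conclusion.** The point holds in a limited form. In the visible text, the on-treatment window does not carve out the planned off-drug gap, so all-causality on-treatment tables count gap events in full for participants who resume capmatinib and only to day 30 for those who do not. With surgery within two weeks and restart at the limit, the difference is 70 or 182 postoperative days against 30 to 16. Actual differences could be anywhere from nil to these values; the documents do not say whether any of the four participants restarted, or when. A reader might infer that the safety analysis is invalid or that non-restarters' events vanish. Neither follows, because the deaths summary, the flagged listing in the protocol and the dated listings in the SAP remain. This is a cheap improvement of low practical weight.

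**What to change.** In the SAP and its table specifications, for the registry AE and SAE tables and the AE listings:

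1. Define on-treatment as two intervals: first dose to last neoadjuvant dose + 30 days, and capmatinib restart to last adjuvant dose + 30 days. Merge them if they overlap. A participant who never restarts has only the first.
2. For restarters, show events that start or worsen in the gap after day 30 in a separate column for the off-drug surgery/chemotherapy interval. Its denominator is the participants who have such an interval.
3. Optionally keep the present overall column alongside. Event counts in the two new columns add up to it; participant counts need not, because one person can appear in both.

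Merely splitting the existing window into phases would not be enough: the surgical phase would still run to restart in one group and to day 30 in the other.

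**Cost.** SAP and table wording, one derived variable and an extra column. The dosing dates needed are already on the dose administration eCRF (Section 6.1.1). Chemotherapy timing is available for context, since Section 6.2.1.1 requires: "Chemotherapy regimen, dosing, start and stop dates must be recorded in the eCRF".

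**Limits.** Counts will be very small. Nothing changes if nobody restarted more than 30 days after the last neoadjuvant dose. Later events in non-restarters cannot be recovered where collection had stopped. If the redacted text or the unseen specifications already hold a phase flag, check it against item 1.
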